7.0 Subject Disposition

The number and percentage of subjects will be summarized for each of the following categories, for overall and by country:

- Subjects enrolled into the study.
- Subjects who discontinued venetoclax – overall and for each reported primary reason.
- Subjects who discontinued the study – overall and for each reported primary reason.

The number and percentage of subjects who discontinued venetoclax will be summarized by reason (all reasons) and by primary reason (per eCRF). Similar summaries will be provided for discontinuations from the study.

The number and percentage of subjects with reported study drug interruptions will be summarized. Reasons for study drug interruptions will be presented in the CSR listings.

8.0 Demographics, Baseline Characteristics, Medical History, and Previous Concomitant Medications

8.1 General Consideration

The ITT population, ITT-BE, and ITT-BN population will be used to summarize demographics and baseline characteristics. The safety population will be used to summarize medical history and previous, concomitant, and post-treatment medications.

8.2 Demographic and Baseline Characteristics

Categorical baseline variables will be summarized with the number and percentage of subjects in each category. Continuous baseline variables will be summarized with descriptive statistics (number of non-missing observations, mean, standard deviation, median, maximum and minimum).

Categorical baseline variables include:

- Sex (male, female)
- Race (White, Black or African American, Asian, and Other)
- Geographic region (US, EUROPE)
- Ethnicity (Not Hispanic or Latino, and Hispanic or Latino)
- Age (< 65, ≥ 65, < 75, and ≥ 75)
- Tobacco use (current, former, never, and unknown)
- Alcohol use (current, former, never, and unknown)
- ECOG performance status (grade: 0, 1, 2)
- LDH (≤ ULN, > ULN)
- Prior number of oncology therapies (1, 2, ≥ 3)
- Previous line of Ibrutinib failure (1, > 1)
- Previous line of Idelalisib failure (1, > 1)
- 17p deletion status (deleted, not deleted, indeterminate)
- Rai stage (0, 1, 2, 3, 4)
- Binet stage (A, B, C)

- IgVH status (mutated, unmutated)
- ZAP-70 (positive, negative, indeterminate)
- CD-38 (positive, negative, indeterminate)
- Beta 2-microglobulin (< 3 mg/L, ≥ 3 mg/L)
- TP53 mutation (yes, no, unknown)
- 11q (deleted, not deleted, indeterminate)
- 13q (deleted, not deleted, indeterminate)
- 12q trisomy (present, not present, indeterminate)
- Absolute lymphocyte count (ALC) (< 25 × 10⁹/L, ≥ 25 × 10⁹/L; < 100 × 10⁹/L, ≥ 100 × 10⁹/L)
- Bulky disease nodes (< 5 cm, 5 cm To 10 cm, ≥ 10 cm)
- Prior BCRi treated (yes, no)
- TLS risk category-US (low, medium, high)
- TLS risk category-ROW (yes, no)
- Hospitalized for TLS prophylaxis before venetoclax (yes, no)

Continuous baseline variables include:

- Age (year)
- Weight (kg) by male and female
- Height (cm)
- Number of prior oncology therapy
- Beta-2 microglobulin (MG/L)
- Lactate dehydrogenase (LDH)
- Absolute lymphocytes count (10⁹/L)
- Bulky disease nodes (cm)
- Duration of BCRI therapy before venetoclax (month)

8.3 Medical History

Medical history data will be summarized and presented using body systems and conditions/diagnoses as captured on the CRF. The body systems will be presented in alphabetical order and the conditions/diagnoses will be presented in alphabetical order within each body system. The number and percentage of subjects with a particular condition/diagnosis will be summarized. Subjects reporting more than one condition/diagnosis within a body system will be counted only once for that body system.

8.4 Previous Treatment and Concomitant Medications

A prior medication is defined as any medication taken prior to the first dose of venetoclax. A concomitant medication is defined as any medication that started prior to the first dose of venetoclax and continued to be taken after the first dose of venetoclax or any medication that started after the first dose of venetoclax, but not after the last dose of venetoclax. The number and percentage of subjects who have taken medications will be summarized by generic drug name for prior medications, concomitant medication, and prior oncology therapies. In addition, the number and percentage of subjects who have taken zero, one, two, three, four, and five or more drugs will be summarized for prior medications, concomitant medications, and prior oncology therapies.

For summaries of concomitant medications, if an incomplete start date was collected for a medication, the medication will be assumed to be a concomitant medication unless there is evidence that confirms that the medication was not a concomitant medication (e.g., the medication end date was prior to the first dose of venetoclax).

A subject who reports the use of two or more medications will be counted only once in the summary of "Any Concomitant Medication." A subject who reports two or more uses of the same medication will be counted only once in the total for the associated generic drug name. Similar rules apply to prior medications as well.

9.0 Venetoclax Exposure and Compliance

The duration of exposure to Venetoclax will be summarized. Duration of exposure is defined for each subject as (last dose date – first dose date) + 1. Duration of exposure will be summarized using the following statistics: sample size (N), mean, standard deviation, median, and range. In addition, the number and percentage of subjects exposed to Venetoclax will be summarized for the following categories of exposure duration: 0 to 5 weeks, > 5 weeks to 8 weeks, > 8 weeks to 12 weeks, > 12 weeks to 16 weeks, > 16 weeks to 20 weeks, > 20 weeks to 24 weeks, > 24 weeks to 28 weeks, > 28 weeks to 32 weeks, > 32 weeks to 36 weeks, > 36 weeks to 48 weeks, > 48 weeks to 60 weeks, and > 60 weeks.

The compliance based on investigator opinion for each subject will be provided in the listing.

10.0 Efficacy Analysis

10.1 General Considerations

No statistical testing will be performed for the efficacy endpoints. Further details on the analysis sets used will be specified in efficacy analyses described below. All efficacy responses were assessed per investigator review.

10.1.1 Definitions for Efficacy Endpoints

Complete Remission Rate (CR + CRi)

Complete response rate, complete remission (CR) or complete remission with incomplete marrow recovery (CRi), will be defined as the proportion of subjects per the 2008 Modified IWCLL NCI-WG criteria as assessed by investigator using the best response at any time during the study. In addition, the 95% confidence interval for complete response rate (CR) rate based on the binomial distribution (Clopper-Pearson exact method) will be provided. Subjects who do not achieve a CR or CRi will be considered to be non-responders in the calculation of complete response rate.

Overall Response Rate (ORR)

ORR (CR + CRi + nPR + PR) will be defined as the proportion of subjects who achieved complete remission (CR), complete remission with incomplete marrow recovery (CRi), nodular partial remission (nPR), or confirmed partial remission (PR) based on the 2008 Modified IWCLL NCI-WG criteria as assessed by investigator using the best response at any time during the study. Confirmatory PR response will be determined by not less than 49 days from the first PR was observed. The corresponding exact 95% confidence interval for the proportion (Clopper-Pearson exact method) will be constructed. Subjects who do not respond will be considered non-responders.

Duration of Response (DOR)

The DOR for a given subject will be defined as the number of days from the day the criteria are met for CR, CRi, nPR, or confirmed PR (whichever is recorded first) to the earliest date that progressive disease (PD) is objectively documented (radiographic or clinical) or death (i.e., $DOR = PD/death/censoring\ date - earliest\ CR/CRi/nPR/PR\ date + 1\ day$). For subjects who have a PR before CR, CRi, or nPR in subsequent visits, the DOR is computed from the earliest PR. If a subject is still responding then the subject's data will be censored at the date of the last available disease assessment prior to the data cutoff date. Only subjects with the iWCLL response criteria will be included in the analysis of DOR. The distribution of the duration of overall response will be estimated using the Kaplan-Meier methodology. Median duration of response will be calculated and the corresponding 95% confidence interval will be presented.

Time to Progression (TTP)

Time to progression for a given subject will be defined as the number of days from the date the subject started venetoclax to the date of earliest PD (radiographic or clinical) (i.e., $TTP = PD/censoring\ date - first\ dose\ date + 1\ day$). If the subject does not experience disease progression then the subject's data will be censored at the date of the last available disease assessment prior to the data cutoff date. If a subject does not have

any post baseline disease assessments, the data will be censored at the first dose date plus 1 day. The distribution of the time to progression will be estimated using Kaplan-Meier methodology. Median time to progression and the corresponding 95% confidence interval will be estimated.

Progression Free Survival (PFS)

Progression-free survival (PFS) will be defined as the number of days from the date of first dose of venetoclax to the date of earliest PD (radiographic or clinical) or death (i.e., $PFS = PD/death/censoring\ date - first\ dose\ date + 1\ day$). If the subject does not experience disease progression or death then the subject's data will be censored at the date of the last available disease assessment prior to the data cutoff date. If a subject does not have any post baseline tumor assessment or clinical assessment for progression, the data will be censored at the date of first dose plus 1 day. Progression-free survival will be analyzed by Kaplan-Meier methodology. Median duration of PFS will be calculated and 95% confidence interval for median duration of PFS will be presented.

Overall Survival (OS)

Overall survival (time to death) for a given subject will be defined as the number of days from the first dose date of venetoclax to the date of the subject's death (i.e., $OS = death/censoring\ date - first\ dose\ date + 1\ day$). All events of death will be included, regardless of whether the event occurred while the subject was still taking any study drug, or after the subject discontinued any study drug. If a subject has not died, then the data will be censored at the date when the subject was last known to be alive prior to the cutoff date. The date of the last known to be alive will be determined by selecting the last available date of the following study procedures for a subject: study visit/contact date, tumor assessment, clinical disease progression, physical examination, vital signs assessment, clinical laboratory collection, study drug, adverse event assessment, concomitant medication assessment, drug or study completion, survival visit, and post treatment therapy assessment. The distribution of the time to death will be estimated

using Kaplan-Meier methodology. Median survival time and the corresponding 95% confidence interval will be estimated.

Minimal Residual Disease (MRD) Response Rate

The rate of MRD response in CLL subjects will be defined as the proportion of CLL subjects who achieved MRD negative status with less than one CLL cell per 10,000 leukocytes (or below 10^{-4}). All subjects with an MRD assessment will be included in the denominator for the calculation of MRD response rate. Minimal residual disease response will be summarized by categories: MRD negative, MRD positive, or MRD unknown/missing. The 95% confidence intervals based on the binomial distribution (Clopper-Pearson exact method) will be provided.

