For any subject who has not experienced progressive disease (PD) at the time of permanent discontinuation of venetoclax, follow-up phone calls will continue until death, discontinuation from the study or upon study completion.

Response criteria definitions are outlined in 2008 Modified IWCLL-WG Criteria for Tumor Response. See [Table 5](#).

For patients with only Partial Remission at Week 48 an additional CT and a bone marrow examination can be done between Week 48 and Week 108 to confirm CR if there is a possibility that a patient is in Complete Remission based on laboratory tests and a disease assessment physical examination.

NOTE: Disease assessments may be performed approximately 7 days prior to the scheduled visit.

Computed Tomography Scans (or Magnetic Resonance Imaging)

A CT scan with contrast will be accepted if previously performed within 35 days prior to the first dose of venetoclax. Otherwise, a CT scan must be performed within the Screening window (28 days) for all subjects. A CT scan will be performed for all subjects at Week 48 to confirm disease response. Contrast-enhanced CT scans including neck, chest, abdomen, and pelvis will be performed to assess response to treatment. A contrast-enhanced MRI of the neck, chest, abdomen and pelvis with a non-contrast CT scan of the chest may be used for subjects in whom a contrast CT is medically contraindicated (i.e., subjects with a severe allergy to CT contrast agents or subjects with impaired renal clearance). Whichever method is used at Screening should be consistently used throughout the duration of the study.

Any CT scan (or MRI) performed as standard of care throughout the study should be captured on the eCRF.

NOTE: CT scans (or MRI) may be performed 7 days prior to the scheduled visit.

Bone Marrow Aspirate and Biopsy

At baseline, a bone marrow aspirate and biopsy are not required; however results should be recorded if available. If the subject achieves a CR by clinical criteria and confirmatory CT scan, a bone marrow aspirate and biopsy will be performed to confirm the CR. Whenever possible the bone marrow aspirate for biomarker MRD assessment should be split from this sample. If a CT scan is performed and does not confirm a CR, a bone marrow biopsy should not be obtained.

Bone marrow aspirates and biopsies performed as standard of care throughout the study should also be captured on an eCRF.

Subject Calendars/Diaries

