5.4 Removal of Subjects from Therapy or Assessment

5.4.1 Discontinuation of Individual Subjects

Each subject has the right to withdraw from the study and/or study drug treatment at any time. In addition, the investigator may discontinue a subject from study drug treatment at any time if the investigator considers it necessary for any reason including:

- The investigator believes it is in the best interest of the subject
- Subject's response to therapy is unsatisfactory, as evidenced by progression of disease while on study drug
- The subject requires other cancer treatment (e.g., radiotherapy, cancer-related surgery as a result of tumor progression, alternate anti-neoplastic agents) during the study period
- unacceptable toxicity
- The subject becomes pregnant while on the study

- drug/protocol non-compliance

The investigator will inform AbbVie prior to discontinuing a subject from the study by contacting the Clinical Team Leader as identified in Section 7.0. All subjects will be included for analysis of safety data. Subjects who withdraw from the study will not be replaced unless they are not evaluable.

Subjects will continue to be followed for unresolved AEs and survival information for any subject who has not experienced PD at the time of venetoclax discontinuation.

Final Visit

Upon study drug discontinuation and/or upon discontinuation from the study, the reason(s) for discontinuation will be recorded in electronic case report forms (eCRFs) and a final visit will be performed. The final visit procedures as listed in [Appendix D](#) should be performed as soon as possible after discontinuation from study drug.

30-Day Safety Follow-Up Visit

A 30-Day Safety Follow-up Visit should be performed approximately 30 days (\pm 3 days) following the last dose of venetoclax. The 30 day safety follow up procedures listed in [Appendix D](#) should be performed.

Post Treatment and Survival Follow-Up Calls

For subjects who discontinue venetoclax therapy, but do not discontinue the study, post treatment follow-up calls will be performed every 6 months (\pm 7 days) for survival information (i.e., disease progression, the date and cause of death, post-treatment cancer therapies, etc.) and will be collected via telephone calls for a period of 2 years and recorded in the eCRFs.

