8.1.2 Efficacy Endpoints

8.1.2.1 Primary Efficacy Endpoints

The primary efficacy endpoint will be complete remission rate (CR + CRi) of the subjects who have not been previously treated with BCRi therapy defined as the proportion of subjects achieving a CR or CRi as their best response (per the investigator assessment) based on IWCLL NCI-WG criteria.

In addition, the ninety-five percent (95%) confidence interval based on binomial distribution will be constructed for the calculated CR rate.

The assessment of response will be performed when all subjects enrolled have completed their Week 48 disease assessment, or after all enrolled subjects have discontinued venetoclax, whichever is earlier. Subjects who have not achieved complete remission (CR + CRi) prior to this time will be considered to be non-responders in the calculation of CR rate.

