Progression-free survival (PFS) will be defined as the number of days from the date of first dose to the date of earliest disease progression or death. All disease progression will be included regardless whether the event occurred while the subject was taking the study drug or had previously discontinued the study drug. If the subject does not experience disease progression or death, then the data will be censored at the date of last disease

assessment. Data for subjects who receive non-protocol CLL therapy prior to disease progression will be censored at the last disease assessment prior to receiving non-protocol therapy. Data for subjects without any disease assessments performed after the baseline visit will be censored at the time of enrollment plus 1 day. PFS will be analyzed by Kaplan-Meier methodology using data for all subjects enrolled. Median time PFS will be calculated and 95% confidence interval for median time PFS will be presented.

Overall survival (OS) will be defined as number of days from the date of first dose to the date of death for all dosed subjects. For subjects who did not die, their data will be censored at the date of last study visit or the last known date to be alive, whichever is later. OS will be analyzed by Kaplan-Meier methodology using data from all enrolled subjects. Median time survival will be estimated and 95% confidence interval for the median time survival will be presented.

The CR rate (CR + CRi) in previously treated BCRi subjects will be assessed based on the 2008 Modified IWCLL NCI-WG criteria. The ninety-five percent (95%) confidence interval based on binomial distribution will be constructed for the calculated CR rate.

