10.2 Efficacy Analyses

Data collected at any point prior to the specified cutoff date during the study will be used in efficacy analyses, unless otherwise specified.

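### The response window for CR + CRi and ORR does not stop at progression or at other CLL therapy, so a remission recorded on another regimen would count as a venetoclax response

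*SAP*

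**What the plan says.** SAP 10.1.1 uses the same phrase for the complete remission rate and for ORR: response is "assessed by investigator using the best response at any time during the study". SAP 10.2 sets the data window: "Data collected at any point prior to the specified cutoff date during the study will be used in efficacy analyses, unless otherwise specified". SAP 10.2.1 applies the rate to the BCRi-naive population (ITT-BN) and adds no further limit.

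Protocol 8.1.2.1 takes the best response up to the analysis time point: "Subjects who have not achieved complete remission (CR + CRi) prior to this time will be considered to be non-responders". It too is silent on progression and on other treatment.

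The protocol does deal with other treatment elsewhere. For PFS, section 8.1.2.2 says "Data for subjects who receive non-protocol CLL therapy prior to disease progression will be censored at the last disease assessment" before that therapy, and TTP has a similar rule. The response endpoints have no counterpart. The SAP's own TTP and PFS definitions do not repeat the rule, so the SAP has no rule on subsequent therapy for response, TTP or PFS.

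The study continues after venetoclax stops: protocol 5.4.1 plans telephone calls every 6 months for 2 years. Protocol 5.3.1.1 also brings unscheduled results into the database: "Any CT scan (or MRI) performed as standard of care throughout the study should be captured on the eCRF", and "Bone marrow aspirates and biopsies performed as standard of care throughout the study should also be captured on an eCRF".

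**The concern.** The primary objective is the efficacy of venetoclax as a single agent. A remission reached on another regimen says nothing about that, yet the definition gives no ground for leaving it out. The programmer would have to count it or devise an exclusion after seeing the data.

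Any error goes one way. A misattributed remission can raise CR + CRi or ORR but never lower them. How often it happens would depend on which sites enter results obtained under the next treatment. Assessment is by the investigator in an open-label study, and no independent review is described that would catch such a case.

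**Working it through.** **The plan's own figures.** Inputs from SAP 4.3: 6% against 12%, exact test, two-sided 5% (upper tail 2.5%).
- n = 250: at least 24 remissions are needed; upper-tail error 1.63%, power 90.0%. This matches the stated 90%.
- n = 190: at least 19 are needed; upper-tail error 2.06%, power 83.1%. This is somewhat above the stated 80%. Over n = 165 to 200, exact power stays at or above 80% from n = 186 on, so 190 is consistent with the plan. The sample size is not in question.

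**What can enter the window.**
- *On venetoclax:* protocol Table 1 excludes other anticancer therapy throughout administration. This route is largely closed.
- *After progression:* protocol 6.1.1.1 says events clearly consistent with progression lead to discontinuation from the study, which narrows this route. It does not close it, because protocol 5.1 plans follow-up for survival as well as for progression where that has not yet occurred, so a progressed subject may still be on study.
- *After stopping without progression (for example, for toxicity):* protocol 5.4.1 keeps the subject in follow-up, post-treatment cancer therapies are recorded, and standard-of-care scans and marrows go on the eCRF. No rule closes this route.

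**Size per case.** Primary population: 1/190 = 0.53 percentage points. The same definition feeds the rate in BCRi-treated subjects (up to 60), where one case among 60 is 1/60 = 1.7 points.

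**Effect on the interval** (Clopper-Pearson, n = 190):

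| CR + CRi | Rate | 95% interval |
|---|---|---|
| 18 | 9.5% | 5.71% to 14.56% |
| 19 | 10.0% | 6.13% to 15.18% |
| 23 | 12.1% | 7.83% to 17.61% |

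One extra case takes the lower limit past 6% only if there are exactly 18 true remissions. That probability is P(at least 18) minus P(at least 19):
- true rate 6%: 3.78% − 2.06% = 1.7%
- true rate 12%: 88.44% − 83.11% = 5.3%

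**Several cases.** Assume k of the 190 are misattributed; the documents give no value for k. With a true rate of 6% in the rest, the chance that the lower limit exceeds 6% is P(at least 19 − k among 190 − k):

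| k | Added to rate | Chance lower limit > 6% |
|---|---|---|
| 0 | 0 | 2.1% |
| 1 | 0.53 points | 3.6% |
| 2 | 1.05 points | 6.1% |
| 3 | 1.58 points | 9.8% |
| 4 | 2.11 points | 15.1% |

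**A consistency check on DOR.** SAP 10.1.1 computes DOR as the earliest progression date minus the first response date plus 1 day. If the first response is recorded after progression, the result is zero or negative. The SAP's own formula therefore needs a response window that closes at progression.

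**The case against.** The strongest reply is that the gap has little room to act. Response is assessed at Weeks 24, 36 and 48, with optional confirmation of CR up to Week 108 for subjects in partial remission. Protocol Appendix D has no disease assessment at the final visit, the 30-day visit or in post-treatment follow-up. CR needs blood counts, examination, absence of symptoms, a negative CT and a negative marrow, so a scan on the eCRF is not yet a recorded remission. The cutoff also shortens exposure: the only row of SAP Table 1 that includes efficacy data is 30 April 2018, about 26 months after the original protocol date of 24 February 2016. All of this stands. It makes cases rare but does not supply the missing rule, since an investigator could still enter a response and nothing would exclude it.

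Three stronger readings are tempting but not supported.
- *Other CLL therapy may be given alongside venetoclax.* A reader might infer this from protocol 5.4.1, where the need for other cancer treatment is only a reason for which "the investigator may discontinue a subject from study drug treatment at any time if the investigator considers it necessary for any reason including", or from the allowance in 5.2.3 for medically necessary medication. But Table 1 excludes anticancer therapy during dosing, and that allowance follows a reference to Appendix C, which is organised by drug interaction.
- *The inflation is several points.* This needs assumed rates of early stopping and of next-line remission. If 5% to 20% of subjects without CR start another therapy and 6% to 30% of those have a CR recorded on it, the excess is 0.5 to 10.7 cases. None of those inputs is in the documents, and the upper end is hard to reconcile with a schedule that has no assessments after treatment.
- *One case can turn a failed trial into a successful one.* SAP 10.1 plans no statistical test, and the crossing needs exactly 18 true remissions.

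**Conclusion.** The point holds as a fault in a stated rule. As written, SAP 10.1.1 counts as a venetoclax response any CR or CRi (and, for ORR, any qualifying response) recorded before the cutoff, including one recorded after non-protocol CLL therapy began, or after progression in a subject still on study. The protocol treats such therapy as a reason to censor TTP and PFS but has no equivalent rule for the primary endpoint.

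The size is 0.53 points per case in the primary rate, upward only. The number of cases is unknown and probably small. The effect is on the estimate, its interval and the informal comparison with 6%; sample size and power are unaffected. This should be fixed, because it concerns the primary definition and costs little, but nothing in the documents shows that it would change the trial's conclusion.

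**What to change.** In SAP 10.1.1, for CR + CRi and for ORR, replace the any-time wording with: *documented after first dose and before the earlier of disease progression and the first non-protocol anti-CLL therapy, up to the data cutoff*. State that the same window governs the first response used in DOR. List later responses separately.

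Protocol 8.1.2.1 does not contain the SAP's phrase, so there the same limit should be added where best response is defined.

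The window has no fixed last visit, so CRs confirmed on venetoclax between Weeks 48 and 108 still count if they precede the cutoff.

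The cost is one sentence in the SAP and one clause in the protocol. Progression dates and post-treatment cancer therapies are already collected, and the protocol's TTP and PFS rule already requires knowing when other therapy began. The reported rate may be slightly lower. While making the edit, the sponsor should also restore the protocol's censoring rule for non-protocol therapy in the SAP's TTP and PFS definitions, or explain its absence.
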